Specific Aims

The diagnostic system that is currently used for mental disorders is based on verbal report, observable behavior, and clinical phenomena that have been aggregated based on statistical approaches to provide reliable categories¹. However, the connection between psychiatric disorders and their underlying neurobiology has been difficult to establish. The NIMH Research Domain Criteria (RDoC) framework is a heuristic approach to integrate neuroscience with psychopathology². Thus, RDoC is the attempt to develop constructs that (a) connect across units of analysis, (b) are applicable across established diagnostic criteria, and (c) are a point of departure to provide measurable constructs to gain a deeper understanding of psychiatric conditions³.

We focus on the positive and negative valence system domains proposed by the RDoC^{4,5}, using self-report, behavior, physiology, and neural circuit unit of analysis measures, apply them to a clinical population of individuals with anxiety or depression recruited from primary care clinics across two sites and apply latent variable analysis to derive latent constructs of positive and negative valence systems functioning that cut across units of analyses. Our preliminary studies provide initial evidence for the relative independence of measures designed to assess each domain. Building on these studies we will adopt a three stage approach: first, principal component analyses will be used for variable reduction within a task; second, confirmatory factor analyses will be used to determine whether the model of positive and negative valence systems fit with the measures obtained from multiple units of analyses; and third, latent variable analysis will be used to relate measures across different units of analysis. The specific aims of the proposal are:

- (1) To recruit, assess, and analyze self-report, behavioral, physiological, and neural circuit unit of analysis data in an exploratory sample of n=100 treatment seeking anxious and/or depressed individuals presenting to primary care clinics at UCSD and UCLA.**
 - a. Hypothesis 1: Measures of reward sensitivity, attentional bias towards positive valenced stimuli, approach behavior in an approach/avoidance task, propensity to display a happy facial expression, increased respiratory sinus arrhythmia (vagal tone), and activation in the ventral striatum during a reward processing task will load together on a latent construct ("Positive Valence System").

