 - b. Hypothesis 2: Measures of high harm avoidance, attentional bias towards negatively valenced stimuli, avoidance behavior in a approach/avoidance task, propensity to display a negative facial expression (e.g., sadness, fear), increased heart rate and skin conductance while viewing negative stimuli, and amygdala activation during a fear conditioning task will load together on a latent construct ("Negative Valence System").
 - c. Hypothesis 3: Latent variable scores of individuals with anxiety or depression will span a two-dimensional space according to these two latent constructs and will show significant variability across DSM IV (or DSM-5) diagnostic categories.
- (2) To obtain a confirmatory sample of n=100 subjects at both sites using the same measurement approaches to determine the reproducibility and robustness of the latent constructs obtained from the exploratory sample.**
 - a. Hypothesis 1: Latent constructs of positive and negative valence systems show good reproducibility in a confirmatory factor analysis.
 - b. Hypothesis 2: Variable reduction can be used to obtain reliable projection onto the latent constructs using latent variable analyses.
 - c. Hypothesis 3: Individuals with clinically severe and impairing anxiety or depression will fall into heterogeneous clusters of dysfunctions within the positive and negative valence systems.
- (3) To obtain a reliability sample of n=50 individuals at UCSD and UCLA that will be re-tested within a month to determine the reliability of the latent constructs.**
 - a. Hypothesis 1: Latent constructs of positive and negative valence systems have good test-retest reliability.
 - b. Hypothesis 2: Latent constructs of positive and negative valence systems have better test-retest reliability than measures from individual units of analyses.

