General Statistical Approach: The goal of this proposal is to derive latent variables that adequately quantify the positive and negative valence domain across different units of analyses. The analysis of the variables that are extracted from each unit (as shown in Figure below) will consist of three steps. First, a principal component analysis will be conducted for each unit of analysis to determine the number of independent degrees of freedom contributing to the variance observed in each unit. For example, we will utilize all facial action units, which have been recorded during viewing of IAPS pictures in a principal components analysis. We expect to extract at least two independent components (as shown in the pilot data sections above). The action units that show the highest correlation with the components will be used for subsequent analyses. Second, we will conduct a confirmatory factor analysis with the variables from each unit of analysis that showed the highest correlation with the principal components and propose two factors – positive valence system and negative valence system. We will subsequently test the statistical significance of the coefficients contributing to the factors. Finally, we will conduct a latent variable analysis as detailed below to relate one unit directly to another unit of analysis.

Unit of Analysis	Measure	Positive System Domain	Negative System Domain
Neural/Circuits	Reward paradigm: BOLD % signal difference during reward or loss trials in anatomically constrained ROIs for (1) Anticipation & (2) Outcome phase	Reward trials - anticipation & outcome phase: Ventral striatum, dorsal striatum (caudate), OFC, amygdala	Loss trials - anticipation & outcome phase: Ventral striatum, dorsal striatum (caudate), OFC, amygdala
	Fear conditioning task: BOLD % signal difference in anatomically constrained ROIs for Conditioning trials (CS+E + CS+U vs. CS-)	n/a	Amygdala, insula
Physiology	HR, SCR, EMG, & RSA while viewing emotional images (IAPs)	RSA/vagal tone - resting state; viewing positive images	HR, SCR, EMG - viewing negative images
Behavior: Facial Expressions	Automatic Facial Action Coding System while viewing emotional images (IAPs)	Positive facial expressions (e.g., AUs 12, 6)	Negative facial expressions (e.g., AUs 4, 15, 1+4, 23, 24)

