$$\eta_{is} = \alpha_s + \sum_{k=1}^l \beta_{sk} \eta_{ik} + \sum_{r=1}^q \gamma_{sr} X_{ir} + \sum_{k=1}^l \tau_{sk} W_{isk} \eta_{ik} + \zeta_{is},$$

data analysis and a priori latent variables are hypothesized prior to an examination of the data. The approach proposed here is to utilize a-posteriori approaches with various latent variable models for the exploratory sample and to transition to the a-priori approach for the confirmatory sample. The goal of this proposal is to develop a heuristic framework that will enable one to combine the different units of analysis in a hypothesis-driven manner. Practically, this translates to establishing different structures that are superimposed on the measurement part and examining statistically whether certain structures provide better explanation of the observed variation than others.

Implementation of the latent variable approach: We will use the implementation of the Linear Latent Variable model provided by the *lava*-package¹²² as part of the R¹¹⁶. This package provides a very general modeling framework, which includes structural equation models and mixed models as important special cases. This model class also allows for non-linear effects of covariates and non-linear parameter constraints. The models are specified independently of data using commands that are similar to standard regression modeling in R. The *lava*-package also includes sophisticated inferential methods such as multi-group analyses, robust standard errors for clustered correlated data, maximum likelihood based inference with data missing at random and inference for indirect and total effects.

Example of latent variable approach relating approach/avoidance task to activation of brain areas during reward paradigm and fear conditioning paradigm: This latent model was created with the *lava* package in R. We assumed that three units of analysis (attentional biases, facial expressions and approach/avoidance behavior) contribute differentially to positive and negative value systems (domains). These latent factors – in turn – determine the degree of activation in ventral striatum (VS) orbitofrontal cortex (OFC) and amygdala (AMY) during reward processing and insula (IN) and amygdala (AMY) during fear conditioning (FC). The regression coefficients can subsequently be used to calculate for each subject the degree of positive and negative valence system “state”, which provides the measure that we termed the deliverable of this project.

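### Aim 2 tests reproducibility without comparing the confirmatory wave with the exploratory wave, so a good fit would not show that loadings or scores replicate

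*Combined protocol and SAP*

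**What the plan says.** Specific Aims, Aim 2, recruits a second wave of 100 to "determine the reproducibility and robustness of the latent constructs obtained from the exploratory sample". Hypothesis 1 gives the test: "Latent constructs of positive and negative valence systems show good reproducibility in a confirmatory factor analysis". No fit index, invariance test, agreement measure or cut-off follows. Hypothesis 2 of the same aim adds that "Variable reduction can be used to obtain reliable projection onto the latent constructs using latent variable analyses".

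The General Statistical Approach sets out the analysis: "The analysis of the variables that are extracted from each unit (as shown in Figure below) will consist of three steps". It begins "First, a principal component analysis will be conducted for each unit of analysis". The variables most correlated with the components then enter a two-factor confirmatory factor analysis (CFA), and the factor coefficients are tested for significance. No step is tied to a wave.

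The section on the linear latent variable approach proposes "to utilize a-posteriori approaches with various latent variable models for the exploratory sample and to transition to the a-priori approach for the confirmatory sample". It does not say that the wave-1 indicators, loadings or scoring weights are carried forward.

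Two further statements show what has to replicate. The Summary closing the Significance section aims to replicate the factor scores in the confirmatory sample. The worked example of the latent variable approach says the regression coefficients are used to compute each person's valence state, and calls that measure the project's deliverable.

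**The concern.** What is promised and what is tested differ. The promise is that scores and coefficients found in wave 1 hold in wave 2. The stated test is a CFA, which asks whether a two-factor pattern describes the data to which it is fitted. If it is fitted to wave 2 alone, the loadings are whatever wave 2 makes them, and good fit is compatible with loadings quite unlike those of wave 1.

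The constructs are meant for a public repository and as a platform for treatment research. A user who applies wave-1 weights to new patients needs to know that those weights carry over, and the plan as written would not show it.

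A smaller matter concerns Aim 1. Its loading hypotheses are tested in the sample that also selects indicators and compares models, so those coefficient tests are not independent of model building.

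**Working it through.** **1. The plan's own figure.** Power and sample size considerations gives a minimum detectable r² of 0.156 for n = 100, 10 explanatory variables, alpha 0.05 and power 0.80. Take the overall F test with 10 and 100 − 10 − 1 = 89 degrees of freedom, f² = r²/(1 − r²) and random regressors (noncentrality f² times a chi-square on 99 df, averaged). This gives a minimum of 0.1559 and power of 0.8002 at 0.156, so the figure reproduces. With n = 200 the same calculation gives 0.080. The plan is therefore sized for analysis of one wave at a time. The figure says nothing about comparing waves.

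**2. What each test restricts.** Use the plan's 10 variables and 2 factors, with each variable on one factor.
- Wave-2-only CFA: 10 × 11/2 = 55 variances and covariances, less 10 loadings, 10 residual variances and 1 factor correlation, leaves 55 − 21 = 34 df. None of these restrictions refers to wave 1.
- Two-group model with free loadings: 2 × 34 = 68 df.
- Two-group model with equal loadings: 10 loadings less one per factor for scaling adds 8 restrictions, giving 76 df.

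Those 8 restrictions are the test of equal loadings, and the plan contains none of them. In large samples a correctly specified two-factor model passes a 5% chi-square fit test about 95% of the time, whatever its loadings are.

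**3. Simulation.** Assumptions: 100 per wave, five indicators per factor, assumed loadings, 60 runs per setting.

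| Situation | Wave-2-only CFA accepted | Two-group test flags a difference |
|---|---|---|
| Loadings identical in both waves | 90–92% | not reported |
| Loadings reversed between waves | 92–95% | 80–100% |

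With 60 runs, the simulation standard error is √(0.92 × 0.08/60) = 3.5 percentage points near 92%, and √(0.80 × 0.20/60) = 5.2 points near 80%. The two acceptance rates cannot be told apart.

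**4. Testing on the data that built the model.** Null simulations used n = 100, 4,000 runs and the 26 facial action units that the plan records.
- Two units chosen by principal components and tested in the same data: 46% false positives.
- The same chosen pair tested in new data: 5.5%.
- Indicators from different units of analysis, each selected within its own unit: 5.4%.

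For a search over K independent candidate links, the error rate is 1 − 0.95^K, which is 9.8%, 14.3% and 22.6% for K = 2, 3 and 5. The plan gives no K, so these values are assumed.

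**The case against.** The best defence is that replication is plainly the intent. Aim 2 names the wave-1 constructs as its target. Wave 2 is assigned an a-priori approach, which the plan defines as set before the data are examined. The two factors and the domain of each measure are fixed in the Aim 1 hypotheses and the table of measures. Aim 1 is already called exploratory, and multi-group analysis is listed among the software's features. All of that stands. It does not close the gap: an a-priori pattern says which variable belongs to which factor, not that loadings or weights agree, and listing a software feature does not commit the study to using it.

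Four stronger readings are tempting, and the documents do not support them.
- A reader might infer that selection and testing use both waves pooled. The text names no wave, and the n = 100 calculation points to per-wave use.
- A reader might infer from Aim 2 Hypothesis 2 that indicators will be reselected in wave 2. The plan leaves that open but does not say so, and it fits poorly with the a-priori wording.
- A reader might infer that the final weights rest on one wave. No section says which data supply them.
- A reader might take a different top-ranked facial action unit in each wave as failure of the construct. Interchangeable markers can swap rank while the construct replicates.

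It is also fair that step 4 does little damage to the core of Aim 1. Those hypotheses concern measures from different units loading together, where selection within a unit leaves the error rate near nominal. The exploratory label is needed for same-unit tests and for the model search.

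Finally, equal loadings plus score agreement is one reasonable package among several. What matters is that some comparison between waves is specified in advance.

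**Conclusion.** The concern holds in this form: the stated Aim 2 test does not compare the waves, so it cannot show that loadings, scores or delivered coefficients replicate. This is more than a missing cut-off, because a fit threshold applied to wave 2 alone would leave the same gap. In the simulation that analysis accepted reversed loadings about as often as identical ones (92–95% against 90–92%), whereas the two-group comparison detected the reversal in 80–100% of runs.

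These sizes rest on assumed loadings, five indicators per factor and few runs. Reversal is also a marked difference, and smaller ones would be harder to detect. The structural argument in step 2 does not depend on the simulation. Nothing here implies that the constructs would fail to replicate, or that the study team intends to refit them. The plan should be amended before wave 2 is analysed.

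**What to change.** 1. State that variable selection and model search are run in wave 1 only, and report the wave-1 coefficient tests as exploratory.
2. Carry the wave-1 indicators, factor assignment and scoring unchanged into wave 2, fixed in writing before wave-2 data are analysed.
3. Define Aim 2 Hypothesis 1 as (a) a two-group CFA, with wave as the group, comparing equal with free loadings, and (b) the correlation in wave 2 between scores from wave-1 weights and scores from refitted weights. State the criterion for each beforehand.
4. Report (b) alongside (a) in every case. With loadings of about 0.4 and 100 per wave, the chi-square difference test is imprecise and should not decide alone.
5. If loadings are equal, the final weights may be estimated on all 200. Standard errors then scale by about √(100/200) = 0.71, a reduction of 29%.

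The cost is a change of wording and slightly more analysis, using the multi-group option already named for the chosen package. Recruitment, measurements and the per-wave minimum detectable r² of 0.156 are unchanged. The downside is that the Aim 1 coefficient tests can be reported only as exploratory.

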The RDOC has identified positive and negative valence systems as constructs that can be used to relate altered neural systems functioning to anxiety and depression. Reward sensitivity, measured via reward-related decision-making paradigms, is viewed as a marker of the positive valence system. Threat sensitivity, measured via fear conditioning paradigms, is viewed as a marker of the negative valence system. The neural underpinnings of reward-related decision-making and fear conditioning are well understood. However, no studies to date have assessed the neural processes of both reward sensitivity and threat sensitivity as units of analysis among a larger set of measures (including cognitive, behavioral and physiological), within samples of anxious or depressed patients that is sufficiently large to generate a robust and reliable dimensional set of variables that quantify the positive and negative valence domains. That is the goal of this proposal. We hypothesize that measures of reward sensitivity, attentional bias towards positively valenced stimuli, approach behavior in an approach/avoidance task, propensity to display a happy facial expression while viewing positive stimuli, increased respiratory sinus arrhythmia (RSA; i.e., vagal tone) and activation in the ventral striatum during a reward processing task will load together on one latent construct (i.e., positive valence). Also, we hypothesize that measures of harm avoidance, attentional bias towards negatively valenced stimuli, avoidance behavior in a approach/avoidance task, propensity to display negative facial expressions (e.g., sadness, fear), increased heart rate, skin conductance, and EMG while viewing negative stimuli, and amygdala activation during a fear conditioning task will load together on a second latent construct (i.e., negative valence). Further, we hypothesize that latent factor scores of individuals with anxiety or depression will span this two-dimensional space. We aim to replicate these latent factor scores in a confirmatory sample, and test the stability of these scores in a test-retest assessment in a smaller subset of the larger sample. Our goal is to create a robust set of variables for measuring positive and negative valence that will become publically available for future research.

B. Innovation

The proposed project is innovative in the following ways:

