We considered various populations based on our prior studies. We have conducted extensive studies in college populations⁶⁷⁻⁶⁹, non-treatment seeking⁷⁰, and treatment seeking⁷¹ psychiatric populations presenting to an Anxiety Disorders Clinic. We opted to identify individuals with anxiety or depression in a primary care setting, which we have used successfully to recruit a significant number of subjects⁷², to maximize generalizability and external validity. Medication status was another important consideration. On the one hand, including medicated individuals with the possibility of using statistical techniques to account for their effect would provide a larger subject pool and could be conceived as being more representative. On the other hand, given our prior studies showing that antidepressants affect brain activation⁷³⁻⁷⁵, a medication-free group would provide a more scientifically compelling approach to delineate the underlying latent constructs reflecting the positive and negative valence systems. Moreover, the former would require a much larger number of subjects and could not rule out a contribution of medication we chose the latter approach as detailed below.

Study clinics and subjects. We will recruit two waves of n=100 individuals each from two clinics (see power analysis): UCSD Primary Care Clinic and the UCLA Family Health Center (n=50 per wave per clinic). The UCLA clinic has 10 faculty physicians and 36 residents, the UCSD clinic is staffed by 40 faculty physicians. Consistent with our prior work⁷², we expect to recruit a sample where ethnic minorities (approximately 40% in the UCLA clinic and 47% at the UCSD clinic) and low-income individuals (approximately 25% at both clinics) are well represented. Assuming equal non-refusal rates across sociodemographic groups, we project a final sample that is 50% female; 86% Caucasian, 6% African-American, 20% percent Hispanic, 6% Asian and 2% other; 25% low-income; and between 1-5% uninsured.

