Subject inclusion and exclusion criteria. To enhance generalizability, and importantly, to enable selection of subjects in keeping with the RDoC intent, this study will feature broad inclusion criteria and narrow exclusion criteria. This approach was selected to maximize the clinical diversity of the study population. **General Inclusion criteria are:** (1) Referred for treatment of anxiety and/or depressive symptoms; (2) Score on the PHQ-9 is 10 or higher⁷⁶ and/or score on the OASIS is 8 or higher⁷⁷; (3) Between the ages of 18-55; (4) Able to provide informed, written consent. Notably, in our prior CALM study, inclusion based on the OASIS plus a DSM-IV anxiety disorder yielded a highly comorbid anxious and depressed sample (approximately 76% had comorbid depression). Thus, we fully expect that inclusion based on elevated anxiety (OASIS) or depression (PHQ-9) scores will yield a sample with the full range of anxiety and depression symptoms and associated functional impairment. **Exclusion criteria include:** The first 7 criteria below closely match procedures we successfully employed in our prior primary care CALM study (1) No telephone or easy access to telephone; (2) Alcohol or marijuana dependence (but not abuse) in the past year; (3) All other drug abuse or dependence in the past year. Subjects with alcohol or marijuana abuse in the past 12 months will be permitted in the study, but also will be given referrals for additional substance abuse treatment which may occur concurrently; (4) Bipolar I or Psychotic disorders; (5) Moderate to severe traumatic brain injury with evidence of neurological deficits, neurological disorders, or severe or unstable medical conditions that might be compromised by participation in the study (to be determined by primary care provider); (6) Active suicidal ideation; (7) Inability to

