speak English; (8) Current use of a medication that could affect brain functioning, e.g., anxiolytics, antipsychotics, antidepressants, or mood stabilizers; (9) MRI exclusions: cardiac pacemaker, metal fragments in eyes/skin/body (shrapnel), aortic/aneurysm clips, prosthesis, by-pass surgery/coronary artery clips, hearing aid, heart valve replacement, shunt (ventricular or spinal), electrodes, metal plates/pins/screws/wires, or neuro/bio-stimulators (TENS unit), persons who have ever been a metal worker/welder, history of eye surgery/eyes washed out because of metal, vision problems uncorrectable with lenses, inability to lie still on one's back for 60 minutes; prior neurosurgery; tattoos with metal dyes, unwillingness to remove body piercings; (10) non-correctable vision or hearing problems, or color blindness, as some cognitive tests require intact sensory functioning. Patients who are excluded from the study will be referred outside of the study for additional care.

Further diagnostic assessment. Although, as noted above, entry into the study is not based on meeting diagnostic criteria for a particular mood or anxiety disorder, it will be important to characterize how our findings map onto DSM (currently DSM-IV, but we will adapt to using DSM-5 criteria, which will become available for the start date of this study). Accordingly, patients will complete a diagnostic interview with study personnel, using an abbreviated version of the Mini International Neuropsychiatric Interview (MINI Version 5.0.0 or its DSM-5 successor, when available)⁷⁸. The MINI was chosen over other diagnostic interviews (e.g., SCID or CIDI) because of its relative brevity, good inter-rater reliability, and suitability for use by an interviewer with limited training, and because we used it in our previous primary care treatment study, CALM⁷², and so we have extensive experience in its training, quality control, use and interpretation. We will include sections on PD, SAD, Posttraumatic Stress Disorder, GAD, OCD, and Major Depression and several modules to provide further clinical information or to determine ineligibility (Suicidality, Manic/Hypomanic Episode, Alcohol Abuse/Dependence, Drug Abuse/Dependence, and Psychotic Disorders).

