Procedures: Patients presenting to the UCSD and UCLA clinics and completed complete the screening measures (OASIS and PHQ-9) are eligible subjects and will be asked to participate via our facilitated referral system. Individuals who accept an invitation to take part in the study will undergo a MINI diagnostic interview. Subjects included in the study will return for a behavioral testing session and a neuroimaging testing session. During the behavioral session participants will complete the self-report assessments, modified probe detection task, approach/avoidance conflict task, and emotional reactivity assessment in which they will view blocks of emotional images while state affect and physiology will be assessed throughout the procedures. The fMRI session will be scheduled within 2 days of the behavioral session and will comprise the following sequence of events: Prior to scanning, each subject will complete (1) informed consent, (2), self-report emotion assessments, (3) review of fMRI procedures and MRI safety screen, (4) review of instructions to complete the fear conditioning and reward tasks, and completion of practice tasks to ensure comprehension of instructions. The scanning protocol will consist of (1) reward processing task, (2) high-resolution structural scan, (3) fear conditioning task. A subset of participants (n=25 from each site) will be invited to return approximately one-month later to complete the same battery of assessments to establish test-retest reliability of the latent constructs (see Specific Aim 3).

Self-report Measures

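### Aim 3 neither records nor separates treatment started between test and retest, so real change may be counted as unreliability; it also invites only as many people as it needs retested

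*Combined protocol and SAP*

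**What the plan says.** **Who is enrolled.** Inclusion criterion 1 is "Referred for treatment of anxiety and/or depressive symptoms". Exclusion criterion 8 is "Current use of a medication that could affect brain functioning", with antidepressants and anxiolytics among the examples. The criterion does not say whether it applies again at the retest. The Sample section explains the choice of a medication-free group: "given our prior studies showing that antidepressants affect brain activation". It adds that statistical adjustment in a medicated sample could not rule out a drug contribution.

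**The retest.** Specific Aim 3 is "To obtain a reliability sample of n=50 individuals at UCSD and UCLA that will be re-tested within a month". The Procedures paragraph says "A subset of participants (n=25 from each site) will be invited to return approximately one-month later to complete the same battery of assessments". The Summary that closes the Significance section describes the same step as a plan to "test the stability of these scores in a test-retest assessment in a smaller subset of the larger sample", and the larger sample is 200: "We will recruit two waves of n=100 individuals each from two clinics".

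**The analysis.** The Test/Re-test Reliability paragraph names standard ICCs, Cronbach's coefficient and Guttman's estimates. It does not give the ICC form, a treatment term, a subgroup or a precision target. Aim 3 Hypothesis 1 is that the latent constructs have good test-retest reliability. Hypothesis 2 is that they are more reliable than measures from single units of analysis.

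**The concern.** A test-retest coefficient measures measurement error only if the people measured have not changed, or have all changed alike. This sample has been referred for treatment and is free of the listed medications at the first visit. Some may start medication or psychotherapy in the following month. The plan gives its own reason to expect that this matters for the imaging measures. Several self-report measures also follow recent state: the PANAS trait version and the MASQ both ask about the past week, and the PHQ-9 and OASIS are in the table of measures.

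Hypothesis 1 could then fail because some participants improved, and not because the constructs are poorly measured. Hypothesis 2 compares quantities that treatment may move by different amounts. If treatment between visits is not asked about at the retest, it may not be recoverable later, and nobody could tell how far it explains the result.

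A second, smaller point is that the number invited equals the number to be retested, so a single non-return leaves Aim 3 below its stated size.

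**Working it through.** **1. The plan's figure.** 25 per site × 2 sites = 50. This reproduces Aim 3's 50, but only if everyone invited returns. No power or precision calculation stands behind the 50.

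**2. Non-return.** No retest non-return rate is given; 5% to 30% is assumed here. Expected number retested = 50 × (1 − d), and invitations needed = 50 / (1 − d), rounded up.

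| Non-return d | Expected retested of 50 | Invitations for 50 |
|---|---|---|
| 5% | 47.5 | 53 |
| 10% | 45 | 56 |
| 20% | 40 | 63 |
| 30% | 35 | 72 |

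The chance that all 50 return is 0.95^50 = 7.7% at 5% non-return and 0.90^50 = 0.5% at 10%. Every figure in the last column can be met from the 200 enrolled.

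**3. Precision.** For two occasions, F = (1 + ICC)/(1 − ICC). At ICC 0.70, F = 1.70/0.30 = 5.667. Divide and multiply F by the 97.5% point of the F distribution with n − 1 and n − 1 df, then convert each result back by (F − 1)/(F + 1).

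| n | 97.5% point | 95% CI for ICC 0.70 |
|---|---|---|
| 50 | 1.762 | 0.53-0.82 |
| 40 | 1.891 | 0.50-0.83 |
| 25 | 2.269 | 0.43-0.86 |

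**4. Effect of treatment on the pooled ICC.** Assume variance 1 at the first visit and covariance 0.70 between visits. A fraction p starts treatment, independently of score, and changes by mean d and SD s (in first-visit SDs). Then:

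- mean change m = p·d
- added variance at the retest v = p(s² + d²) − m²
- consistency ICC = 2(0.70)/(2 + v)
- agreement ICC = 2(0.70)/(2 + v + m²)

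| p | d | s | m | v | Consistency | Agreement |
|---|---|---|---|---|---|---|
| 10% | 0.3 | 0.3 | 0.03 | 0.0171 | 0.69 | 0.69 |
| 20% | 0.3 | 0.3 | 0.06 | 0.0324 | 0.69 | 0.69 |
| 30% | 0.5 | 0.5 | 0.15 | 0.1275 | 0.66 | 0.65 |
| 50% | 0.5 | 0.5 | 0.25 | 0.1875 | 0.64 | 0.62 |
| 50% | 0.8 | 0.6 | 0.40 | 0.34 | 0.60 | 0.56 |
| 100% | 0.5 | 0 | 0.50 | 0 | 0.70 | 0.62 |

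The values of p, d and s are all assumptions. The last row shows why the ICC form matters: a uniform shift leaves consistency untouched and lowers only agreement.

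**5. Direction.** Step 4 lets treatment start at random. In a simulation where half start treatment, in a pattern tied to first-visit level that widens the spread, the test-retest correlation rose from 0.70 to about 0.71. When those with higher scores were likelier to start and then dropped by 0.5 SD, it fell to about 0.64. A fall is the more plausible result, but it is not guaranteed.

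**The case against.** A reader might infer that Aim 3 reliability is biased down and that the retest sample is short. The documents establish neither. They give no uptake of treatment within a month, no size of change, no retest attrition and no ICC form. Under mild assumptions 0.70 moves only to 0.69, and the lowest value, 0.56, is an agreement ICC at the extreme of the assumed range, where consistency is 0.60. This objection stands, and the conclusion is worded to match.

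The invitation sentence may be loose wording for 25 per site who return, and nothing forbids replacing non-returners. A 20% loss moves each confidence limit by less than 0.03. That also stands: the two statements need reconciling, but little precision is at risk.

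A reader might also infer that reliability should be estimated only in those with no new treatment. The plan does not support that either. Stability in treatment-seeking patients is a legitimate target, given the stated priority on generalizability. If starting treatment is related to severity, the remaining participants are selected after baseline and may differ in range and in ICC. At 20% to 50% uptake only 40 to 25 of 50 pairs would remain.

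For Hypothesis 2 no direction can be claimed, because the latent scores are built from the same measures that treatment may move.

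None of this removes the gap. The plan does not say that treatment between visits will be recorded, and without that record nobody can tell which case applied.

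**Conclusion.** The point holds as a gap in the design and analysis of Aim 3. As written, the plan can count real change as unreliability, in a sample chosen because it is referred for treatment and kept free of medication for the very reason that drugs alter the measures. With a treatment-free ICC of 0.70, the illustrative loss runs from about 0.01 to 0.14. It depends wholly on assumed uptake and response and on which ICC is used, and a small rise is possible. Hypothesis 2 may be distorted in either direction. The match between 50 invited and 50 required is a real inconsistency of minor consequence. The change is worth making because it is cheap and the information may be lost if it is not collected at the retest.

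**What to change.** 1. At the retest visit, record any medication or psychotherapy started since the first visit.
2. State the ICC form (consistency or agreement) and the interval method in the Test/Re-test Reliability paragraph.
3. Report the Aim 3 reliability estimates, with intervals, for all retested participants and for those with no new treatment, and interpret Hypotheses 1 and 2 in the light of both.
4. In the Procedures, replace the fixed number invited with invitations to those already enrolled until 25 per site have completed both visits.

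**Cost.** One question, one extra analysis and a few more invitations (53 to 63 in all at 5% to 20% non-return), with no more than the planned 50 completed retests. The no-new-treatment estimate will be less precise (0.43-0.86 at n=25 for ICC 0.70) and comes from a subset selected after baseline, so it should stand beside the all-participant estimate and not replace it. The change records and reports only; no one's treatment is altered.
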